7.2 Concomitant Therapy

Subjects will be instructed to inform the investigator prior to starting any new medications from the time of first dose of study treatment until the end of the study.

At each study visit subjects should be asked: “Have you taken any new medicines, other than those provided in this study, since your last visit/contact?” or “Has your child needed to take any medicines, other than those provided in this study, since his/her last visit/contact?”.

All medications (other than trametinib) including non-prescription medication(s), vitamins and herbal product(s), taken during the study will be recorded in the CRF. Any significant non-drug therapies should also be noted in the subject’s CRF.

Subjects should receive all necessary supportive care during the study.

Examples of permissible concomitant therapies:

- Transfusions of blood and blood components
- Pain relief medication
- Anti-infective medications (see prohibited and cautioned medications in [Section 7.2.1 and 7.3](#)). Investigators should discuss prescription of anti- fungal, anti-viral agents with Novartis.
- Treatment for concomitant medical conditions, adverse events (see prohibited and cautioned medications in [Section 7.2.1 and 7.3](#))
- Supplemental nutrition (enteral, parenteral)
- Routine vaccinations including live vaccines as needed based on subject age
- Supportive care use of anticoagulants and compression garments is allowed. Subjects must have been using these interventions in an unchanged manner for 30 days before study enrollment
- Replacement therapy (e.g., thyroxine, insulin, or physiologic or stress doses of corticosteroid replacement therapy for adrenal or pituitary insufficiency, etc.) are permitted. Steroid premedication for imaging scans is allowed.

7.2.1 Permitted concomitant therapy requiring caution and/or action

As trametinib is metabolized predominantly via deacetylation mediated by hydrolytic enzymes(e.g. carboxylesterases), its pharmacokinetics are unlikely to be affected by other agents through metabolic interactions. Trametinib repeat-dose exposure was not affected by co administration with a CYP3A4 inducer. Based on in vitro and in vivo data, trametinib is

unlikely to significantly affect the pharmacokinetics of other medicinal products via interactions with CYP enzymes or transporters.

Please refer to the latest version of trametinib IB for additional information pertaining to trametinib⁶³.

7.3 Prohibited medication

No other cancer chemotherapy, radiotherapy, or immunomodulatory agents including mTOR inhibitors will be permitted while on treatment with study drug. Agents must not be given within 30 days of study drug initiation.

7.4 Rescue Medication Administration

Supportive care measures including but not limited to antimicrobials, topical steroids, antiemetics, blood products, fluids, electrolytes, albumin infusions, immunoglobulin infusions will be permitted while on study as rescue medications for adverse events or other causes (acute hypotension, acute or chronic anemia, acute or chronic hypoalbuminemia, acute infection, etc.). Decision for supportive care will be administered per the provider's discretion at the time subject presents with symptoms or signs requiring escalation of care (emergency department, urgent care, inpatient setting, primary provider).

8 STUDY EVALUATIONS AND MEASUREMENT

8.1 Schedule of Assessments

The schedule of assessments [Table 8-1](#) lists all the assessments to be performed as part of the study, an "X" in the table indicates the visit(s) when they are to be performed.

All data obtained from these assessments must be supported in the subject's source documentation.

Subjects should be seen for all visits/assessments as outlined in the assessment schedule ([Table 8-1](#)) or as close to the designated day/time as possible. Missed or rescheduled visits should not lead to automatic discontinuation. Subjects who prematurely discontinue the study for any reason should be scheduled for a visit as soon as possible, at which time all of the assessments listed for the end of treatment visit will be performed. At this visit, all dispensed investigational product should be reconciled, and the adverse event and concomitant medications recorded on the eCRF.

During the course of the study, test procedures should occur on schedule whenever possible as per allowable visit. For Cycles 1-3, the window is +/- 3 days; for all other cycles, the window is +/- 7 days.

If the COVID-19 or other pandemic limits or prevents on-site study visits, alternative methods of providing continuing care may be implemented. Phone calls or virtual contacts (e.g. teleconsultation), can replace on-site study visits, for the duration of the pandemic until it is safe for the subject to visit the site again.

Table 8-1 Schedule of Assessments

Footnotes:

Day¹: Cycles 1-3: +/- 3 days; Cycles 6-24: +/- 7 days

Laboratory studies²: as outlined in section [6.1 Screening Assessments](#)

Urine or serum pregnancy³: as outlined in section [6.1 Screening Assessments](#)

ECG⁴: repeat during the study if abnormal at screening or as clinically indicated per treating team (not triplicate)

X⁴: repeat during the study if abnormal at screening or by decision of the treating team (not triplicate)

Ophthalmologic exam⁵: As outlined in section [6.1 Screening Assessments](#)

Radiologic assessment⁶: At screening and at the end of every cycle 6 cycles on treatment are mandatory.

Following radiologic assessments as per decision of local treating team

X⁷: Within 4 weeks (28 days) of screening

Optional Biologic Studies⁸: As outlined in section [6.1 Screening Assessments](#)

X⁹: All labs, physical exams, and vital signs, must be done within 14 days of starting Trametinib

X¹⁰: If applicable, dependent on treating team

8.1.1 Medical Record Review

The following will be abstracted from the medical chart (paper or electronic):

- Demographic characteristics (age, gender, race, ethnicity)
- Location/locations of vascular anomaly
- Histologic Diagnosis
- Diagnostic vascular anomaly data
- Vascular Anomaly Past Medical History including:
 - Surgical procedures
 - Interventional Radiology procedures
 - Prior vascular anomaly directed medical therapy (medication, dates, response)
- General Past Medical History:
 - Diagnoses and relevant dates
 - Surgeries and relevant dates
 - Medications
- Current laboratory testing (within 14 days of screening)
- Current radiologic assessment

8.1.2 Physical Examination

General physical examination will include assessments of the following systems: General, Head/Ears/Eyes/Nose/Throat (HEENT), Respiratory, Circulatory, Abdominal, Neurologic, Musculoskeletal, Dermatologic, Lymphatic, Psychiatric, and Dental exam.

8.1.3 Vital Signs

Vital signs to be collected per institutional age-appropriate standards: Height, Weight, Temperature, Pulse, Respiratory Rate, Blood pressure, and Pulse Oximetry.

8.1.4 Laboratory Evaluations

- Blood sampling will be performed per institutional standards.
- Laboratory studies as outlined in section [6.1 Screening Assessments](#).

8.1.5 Pregnancy Testing

Pregnancy testing as outlined in section [6.1 Screening Assessments](#).

8.1.6 Other Evaluations, Measures

- Echocardiogram: As outlined in [6.1 Screening Assessments](#).
- Electrocardiogram (ECG): As outlined in [6.1 Screening Assessments](#).
- Ophthalmologic examination: As outlined in [6.1 Screening Assessments](#).

8.2 Efficacy Evaluations

The optimal measure of disease response in subjects with complex vascular anomalies has not been established. Current practice includes changes in physical exam, radiographic (MRI) evaluations, laboratory assessments and/or quality of life measures. These lesions are difficult to assess with any one method because of heterogeneity in growth patterns, diversity of associated clinical and laboratory abnormalities and a fluctuating clinical course dependent upon factors other than treatment, such as intercurrent infections, puberty, and trauma. It is currently unclear if there is a good correlation between lesion size, determined radiographically and clinical changes or quality of life measures. For these reasons we have elected to assess disease response using three distinct criteria generating a single composite assessment or Individualized Response Criteria:

Radiologic Response	PROMIS	Assessment of Clinical Benefit (examples)
-MRI (recommended) -MRL (see notation below) -CT Scan -US -Xray -Dexascan	See below (8.2.2)	Parameters for grading the Clinical Benefit Assessment (Appendix X) Examples of testing or assessments that can be followed to complete this grading scale include: 
 ○ Pulmonary function testing ○ Lymphedema staging ○ Laboratory parameters ○ Bleeding assessment ○ PLE grading ○ Effusion assessment ○ Infection rates ○ Seizure grading ○ Photography ○ Videos ○ Patient narratives

8.2.1 Radiographic Response

8.2.1.1 MRI/MRL:

MRI or MRL imaging will be recommended as primary imaging modality for all subjects enrolled in VATCH sub-protocols. For subjects with disease manifestation better characterized by alternative quantitative imaging modality (i.e. X-ray or ultrasound) this may be substituted and used as alternative imaging. MRI or MRL is the preferred method of imaging. MRI/MRL imaging will be done at screening and at the end of cycles 6, 12, and 24 on treatment. Additional assessments can be performed in accordance with the local institutional practice. For each imaging assessment timepoint initial radiographic response will be reviewed by each site's radiologist.

When possible and appropriate, volumetric imaging will be used in combination with standard vascular MRI protocols to assess vascular anomaly response. MRI will be performed using a 1.5 Tesla system (HDX 15.0 series MRI, GE and Espree B-15 series MRI, Siemens). Coronal and axial fast spin-echo T2-weighted sequences will be performed with and without fat suppression. Up to 3 lesions should be identified as target lesions and recorded and measured at screening. Target lesions should be selected on the basis of their size and their suitability for accurate repeated measurements (either by imaging techniques or clinically). The same method of assessment and the same technique should be used to characterize each target lesion at screening and during follow up ([APPENDIX VI](#)).

8.2.1.2 Other Radiographic Assessment

Other imaging modalities including, but not limited to Computed tomography (CT) Scan, Ultrasound (US) or X-ray may be utilized for radiographic assessment criteria either in supplement to or in replacement of MR imaging as noted above. Target lesions should be selected on the basis of their size and their suitability for accurate repeated measurements (either by imaging techniques or clinically). The modality and imaging methods will be determined for enrollment screening and the same method of assessment, and the same technique, should be used to characterize each target lesion at screening and during each imaging follow up. Examples of imaging would be X-Ray for bone disease, ultrasound for pleural effusions, dexascan for lymphatic anomalies with bone lesions, and US (contrast or non-contrast for superficial lesions to assess size and other characteristics such as flow.

8.2.2 Assessment of Patient Reported Outcome Measures (PROMs)

Quality of life is an essential component of high-quality clinical care.⁵³ The Patient Reported Outcomes Measurement Information System (PROMIS) is a validated parent/patient-reported scoring system that was developed with the National Institutes of Health (NIH) that can compare values across a variety of medical conditions.^{33,34} PROMIS is validated in individuals aged 8 years and older.⁵⁶⁻⁵⁸ A caregiver proxy report for the PROMIS measure is also available for use in children; for individuals younger than 8 years old, assessments must be completed by a caregiver proxy. PROMIS is considered to be the gold standard for HRQOL measurement in clinical trials. The recall timeframe for each question includes the past week.

Each question has five response categories. A raw score can be calculated for each PROMIS subscale. Raw scores are then translated into a T-score metric with mean of 50 (standard deviation of 10). A higher PROMIS T-score represents more of the concept being measured. Additional details for scoring and measure interpretation are available at <https://www.healthmeasures.net/score-and-interpret/interpret-scores/promis>. Higher scores represent better functioning. A difference or change in score of three points on the PROMIS Pediatric scale is considered a minimally important difference (MID).

In consultation with subjects, patient advocates, clinicians, and psychometricians, we will use global health measures as the **primary outcome** and pain interference as the **secondary outcome**. For exploratory outcomes, we will administer PROMIS measures for fatigue, anxiety, and depression. This survey battery will be administered every 6 cycles, starting at enrollment and continuing during participation in the study.

For subjects **18+ years old at enrollment**, please refer to “Adult subject 18+ y/o” column in [Table 8-3](#). In total, this battery of measures will include **26 items**. We will also include 2 open-ended questions for exploratory analysis: 1) What positive or negative changes have you noticed since you started taking the medication? 2) What else would you like us to know? For adults with cognitive impairment, guardian/LAR may provide proxy answers for the surveys at the discretion of the study chair and co-chair on a case-by-case basis.

For subjects **8-17 years old at enrollment**, please refer to “Pediatric Subject 8-17 y/o” column in [Table 8-3](#). In total, this battery of surveys will include **43 items**. We will also include 2 open-ended questions for exploratory analysis: 1) What good or bad changes have you noticed since you started taking the medication? 2) What else do you want us to know? For subjects aged 8-17 years old at enrollment, we will simultaneously administer subject-report and proxy-report surveys. (see next paragraph for proxy measures)

For subjects **5-17 years old at enrollment**, please refer to “Parent Proxy 5-17 y/o” column in [Table 8-3](#). In total, this battery of surveys will include **41 items**. We will also include 2 open-ended questions for exploratory analysis: 1) What positive or negative changes have you noticed since your child started taking the medication? 2) What else would you like us to know?

For subjects **1-5 years old at enrollment**, please refer to “Parent Proxy 1-4y/o ” column in [Table 8-3](#). In total, this battery of surveys will include **16 items**.

If subjects change age category after enrollment, they will continue using the same measures from their time of enrollment, rather than switching measures.

Table 8-3

Construct	Adult Subject 18+ y/o	Parent Proxy 1-5 y/o	Parent Proxy 5- 17 y/o	Pediatric Subject 8-17 y/o

Primary Outcome for Individualized Response				
Global Health – Physical Health Subscale	PROMIS Scale v1.2 - Global Health	PROMIS Early Childhood Parent-Report Scale v1.0 - Global Health 8a	PROMIS Parent Proxy Scale v1.0 - Global Health 7+2	PROMIS Pediatric Scale v1.0 - Global Health 7+2
Secondary Outcome for Individualized Response				
Pain Interference	PROMIS Short Form v1.1 - Pain Interference 4a	N/A	PROMIS Parent Proxy SF GenPop v3.0 - Pain Interference 8a	PROMIS Pediatric SF GenPop v3.0 - Pain Interference 8a
Exploratory Outcomes				
Fatigue	PROMIS Short Form v1.0 - Fatigue 4a	N/A	PROMIS Parent Proxy SF GenPop v3.0 - Fatigue 10a	PROMIS Pediatric SF GenPop v3.0 - Fatigue 10a
Anxiety	PROMIS Short Form v1.0 - Anxiety 4a	PROMIS Early Childhood Parent-Report Short Form v1.0 - Anxiety 4a	PROMIS Parent Proxy SF GenPop v3.0 - Anxiety 8a	PROMIS Pediatric SF GenPop v3.0 - Anxiety 8a
Depression	PROMIS Short Form v1.0 - Depression 4a	PROMIS Early Childhood Parent-Report Short Form v1.0 - Depressive Symptoms 4a	PROMIS Parent Proxy SF GenPop v3.0 - Depressive Symptoms 6a	PROMIS Pediatric SF GenPop v3.0 - Depressive Symptoms 8a

*For adults with cognitive impairment, guardian/LAR may provide proxy answers for the surveys at the discretion of the study chair and co-chair on a case-by-case basis.

8.2.3 Assessment of Clinical Benefit

A set of clinical benefit assessments will supplement the radiographic and the PROMIS measures. The clinical benefit assessment tools will be determined at initial screening evaluation for the subject. The same clinical benefit assessment tools will be completed at enrollment and then every 6 cycles for the duration of the study. The investigator will determine the clinical benefit assessment and have this reviewed by the study PI if no radiologic assessment is noted. See [Appendix X](#).

8.2.3.1 Photography/Videos

Assessment with photography and video evaluation can be performed if clinically relevant. If selected as a clinical benefit assessment at initial screening evaluation for the subject this will be documented and obtained as part of enrollment screening. Photography will be obtained at each assessment. Images will be obtained per institutional standard for inclusion into the medical record. Photography under the same conditions and positioning to allow for accurate quantification and qualification on lesional changes is recommended.

8.2.3.2 Patient Narratives

To capture patient narratives, we will administer 5 open-ended questions along with the patient-reported outcome measures at the 6-month time point. Participant responses will be reported in the electronic data capturing system. The questions are listed below.

The study team would like to learn how this medication has affected you. We are interested in any changes caused by the medication. Below, the questions will be about how the medication has affected your vascular anomaly and your overall health. You can skip questions that do not apply to you, or you can respond “none”.

- 1. How has your vascular anomaly gotten better since starting on medication? It is okay to write “none” if nothing has gotten better.**
 - a. How has the rest of your health gotten better since starting on medication in this study? It is okay to write “none” if nothing has gotten better.**
- 2. How has your vascular anomaly gotten worse since starting on medication? It is okay to write “none” if nothing has gotten worse.**
 - a. How has the rest of your health gotten worse since starting on medication in this study? It is okay to write “none” if nothing has gotten better.**
- 3. What else would you like us to know about your experience taking this medication**

8.3 Assessment of Overall Response

8.3.1 Definitions

Evaluable for Toxicity: All subjects will be evaluable for toxicity from the time of their first study drug treatment.

Evaluable for Objective Response: Only those subjects have received at least one therapy cycle and have had their disease re-evaluated will be considered evaluable for response. These subjects will have their response classified according to the definitions stated below. (Note: Subjects who exhibit objective disease progression prior to the end of Cycle 1 will also be considered evaluable for response.)

Target Lesions: All measurable lesions up to a maximum of three lesions total (and a maximum of two lesions per organ) representative of all involved organs should be identified as target lesions and recorded and measured at screening radiographic assessment

or clinical photograph. Target lesions will be selected on the basis of their size (lesions with the longest diameter) and their suitability for accurate repeated measurements (either by imaging techniques or clinically). A sum of the longest diameter (LD) for all target lesions will be calculated and reported as the baseline sum LD. The baseline sum LD will be used as reference by which to characterize the objective lesion response.

Nontarget Lesions: All other lesions (or disease sites), including any measurable lesions over and above the three target lesions should be identified as nontarget lesions and should also be recorded at screening. It is possible to record multiple nontarget lesions involving the same organ as a single item on the case record form (e.g., “multiple enlarged pelvic lymph nodes” or “multiple liver lesions”). Bone lesions may be measurable if ≥ 1 cm on MRI. Measurements of these lesions are not required, but the presence or absence of each will be noted throughout follow-up.

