Efficacy Evaluations	
1. Radiologic assessment (if applicable):
 
 - For subjects with radiologically evaluable disease only. Subjects without radiologically evaluable disease may have a CBA substituted for radiologic evaluation. -MRI evaluation will be at screening, and at the end of cycle 6, 12, and 24 (if applicable) on treatment. If there are signs of worsening, earlier assessment should be done. 
2. Patient reported outcome (PRO) measurements:
 
 - Screening to end of study- Every 6 cycles 
3. Clinical Benefit Assessment (CBA):
 
 - Screening to the end of study- every 6 cycles
Safety Evaluations	
Safety assessments will be conducted through the study (according to the assessment schedule)
 
 • Monitoring of adverse events (AEs) and serious adverse events (SAEs) • Physical examination • Body weight and vital signs • Height and body mass index (BMI) • Karnofsky/Lansky performance status • Laboratory assessment including hematology, biochemistry, urinalysis, and coagulation. • Serum or urine pregnancy test for subjects of child-bearing potential • Echocardiography

- Ophthalmologic exams

Statistical and Analytic Plan

For all the analyses, subjects who received any dose of trametinib will be included in the analyses. For the primary efficacy endpoint of objective response at the end of cycle 6, we will test a null hypothesis of response of 40% against an alternative hypothesis of response rate of 65%. We will follow the Simon's optimal two-stage design: an interim analysis will be conducted after 16 subjects have been observed for response, and if 6 or fewer intermediate, substantial, or stable responses are observed, the trial will be stopped for futility; otherwise, the trial will continue to enroll a total of 39 subjects and at the end of the trial if 20 or more responses are observed, the treatment will be declared promising. This design provides $\geq 90\%$ power when the true response rate is 65% and yields a one-sided type I error of ≤ 0.05 when the true response rate is 40%.

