4.7.2 Total Number of Study Sites/Total Number of Subjects Projected

The study will be a multi-site trial through the CaNVAS Consortium which currently comprises 25 sites throughout the United States.

Recruitment will stop when 39 evaluable subjects are enrolled. It is expected that approximately 45 subjects will be enrolled to produce 39 evaluable subjects.

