9.1 Sample Size and Power

For the primary efficacy analysis of objective response at the end of cycle 6, we will test a null hypothesis of response of 40% against an alternative hypothesis of response rate of 65%. We will follow the Simon's optimal two-stage design: an interim analysis will be conducted after 16 subjects have been observed for response, and if 6 or fewer response is observed, the trial will be stopped for futility; otherwise the trial will continue to enroll a total of 39 evaluable subjects and at the end of the trial if 20 or more responses are observed, the treatment will be declared promising. This design provides $\geq 90\%$ power when the true response rate is 65% and yields a one-sided type I error of ≤ 0.05 when the true response rate is 40%.

For evaluating of toxicity, a sample size of 39 provides 86% probability to observe at least one toxicity event when the underlying true toxicity rate is 5%, so that we have good confidence to observe a rare toxicity type. In addition, this sample size provides a reasonable precision on the estimate of the toxicity rate. For example, with 7 observed toxicity events

out of 39 subjects, the estimated toxicity rate is 18%, with the 95% exact confidence interval (CI) as 8% - 34%.

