9.3 Statistical Analyses Plan

For all the analyses, subjects who received any dose of trametinib will be included in the analyses. The primary efficacy endpoint is objective response (including both response and partial response) at the end of cycle 6 and the primary safety endpoint is toxicity of trametinib. We will use binomial distributions to estimate the response and the toxicity rates with their 95% exact CIs. For the second primary efficacy endpoint of responses at the end of cycles 12 and 24, the response rate will also be calculated with 95% CI. For the secondary endpoint of duration of response, time from initial response to disease progression will be examined, and subjects will be censored at the last adequate disease assessment if no progression occurred by that time. We will use the log-rank tests and/or Cox proportional hazard regression to analyze the endpoint. Should the data suggest the violation of the

proportional hazard assumption, we will consider an alternative method such as accelerated failure time model analysis.

Secondary data analyses will be performed for the secondary outcomes of longitudinal measurements of radiologic assessment, PROMIS Patient Reported Outcome measurements, and Clinical Benefit Assessments, taken at screening, and at the end of cycles 6, 12, 18, and 24. The longitudinal data will be analyzed separately at each follow-up time point and together longitudinally. The paired t-test will be used to look at changes in these measures from pre-treatment levels to the post-treatment level (follow-up at cycle 3) to evaluate the treatment's short-term effects. Mixed effects models will be used for longitudinal analysis to evaluate changes in these measures over time. Should the data suggest the distributions of the measurements deviate from normal distributions, we will consider nonparametric alternatives such as Wilcoxon signed rank test or transformation. Relationships between PROMIS measures and other variables such as pain will be investigated using correlation analysis. Lastly, exploratory analyses will be performed for biomarker measures such as cell-free DNA. Descriptive statistics will be generated to summarize data.

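### The plan gives two populations for the primary two-stage decision (39 evaluable subjects, or everyone dosed) and does not say how a dosed but non-evaluable subject counts against the threshold

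*Protocol*

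**What the plan says.** Two populations are laid down for the same decision.

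- **Evaluable subjects.** Section 8.3.1 says: "Only those subjects have received at least one therapy cycle and have had their disease re-evaluated will be considered evaluable for response". A note there adds back subjects with objective progression before the end of Cycle 1, and no one else. Section 9.1 sets the first stage ("an interim analysis will be conducted after 16 subjects have been observed for response, and if 6 or fewer response is observed") and then states "otherwise the trial will continue to enroll a total of 39 evaluable subjects", with 20 or more responses needed at the end. Section 4.7.2 stops recruitment once 39 evaluable subjects are in: "It is expected that approximately 45 subjects will be enrolled to produce 39 evaluable subjects".
- **All dosed subjects.** Section 9.3 opens with "For all the analyses, subjects who received any dose of trametinib will be included in the analyses". The statistical paragraph of the synopsis repeats this, and its own account of the design reads "the trial will continue to enroll a total of 39 subjects", without the word evaluable.

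On when disease is re-evaluated, the synopsis and the treatment schema put PROs and CBA at the end of every 6 cycles, and imaging at the end of cycles 6, 12 and 24. Earlier assessment is called for on signs of worsening. Section 8.1 asks that anyone who discontinues early be seen as soon as possible for the end-of-treatment assessments.

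**The concern.** The primary result is a count compared with a fixed threshold, so the plan must fix who can enter the count. Here it gives two answers. Neither says what happens to a subject who was dosed but is not evaluable under 8.3.1. That subject could be a failure within the denominator, or could be left out and replaced.

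The choice is not neutral. Under 8.3.1, a subject who stops for toxicity or withdraws in Cycle 1 without progression is not evaluable. Because enrolment runs until 39 are evaluable, someone else takes that place. A subject who progresses in the same cycle stays in as a failure. Exclusion is therefore linked to one way in which treatment fails, and the response rate among those left can sit above the rate among those treated.

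The trial is open-label (section 2.1) and response is judged by the local investigator (section 8.3.2). If the population is settled only after responses are known, the choice itself can decide the result. It should be settled before the 16-subject interim.

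**Working it through.** **Inputs.** From section 9.1: p0 = 0.40, p1 = 0.65, stage 1 n1 = 16, stop at 6 or fewer responses, N = 39, promising at 20 or more; stated one-sided type I error at most 0.05 and power at least 90%. From section 4.7.2: about 45 enrolled for 39 evaluable, so 6/45 = 13.3% not evaluable.

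**Formula.** With stop limit r1 and success threshold r,

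P(promising | p) = Σ over x from r1+1 to n1 of Bin(x; n1, p) × P[Bin(N − n1, p) ≥ r − x].

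**Step 1. The plan's own figures, 39 subjects, nobody missing.**

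| Rule | p = 0.40 | p = 0.65 |
|---|---|---|
| Printed: stop ≤ 6/16, success ≥ 20/39 | 0.093 | 0.958 |
| Stop ≤ 7/16, success ≥ 21/39 | 0.046 | 0.901 |

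The printed rule misses its stated 0.05 with complete data. A search for the Simon optimal design at these inputs returns the second row. That boundary error is a separate matter, so the steps below use 7/16 and 21/39 to isolate the effect of the population.

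**Step 2. Evaluable set, 40% as the null among evaluable subjects.** P(promising) = 0.046. The population rule adds no error.

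**Step 3. Evaluable set, 40% as the rate among all dosed.** Assume that k replaced subjects were dosed and were non-responders. The rate among the evaluable is then 0.40 × (39 + k)/39.

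| k | Evaluable rate | P(promising) |
|---|---|---|
| 1 | 0.40 × 40/39 = 41.0% | 6.0% |
| 2 | 0.40 × 41/39 = 42.1% | 7.7% |
| 3 | 0.40 × 42/39 = 43.1% | 9.7% |
| 6 | 0.40 × 45/39 = 46.2% | 17.8% |

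**Step 4. All-dosed set.**

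- 45 dosed, 40% of them responding, threshold left at 21: 13.5%.
- 45 dosed, 7/16 then 24/45: type I error 0.039; power 0.91 at 65% of all dosed.
- 39 dosed and no more, unassessed subjects counted as failures: type I error stays at 0.046 for a 40% rate among dosed, and the cost is power. If 65% of the assessed respond and 13.3% are unassessed, the dosed rate is 0.65 × 39/45 = 56.3%.
- Power at 56.3%: 0.614 with 21/39 and 0.627 with 24/45.

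**The case against.** A reader might infer that the conflict itself breaks the stated error rate on either reading. The documents do not support that. The printed boundaries already miss 0.05 with complete data. With corrected boundaries, the evaluable reading holds 4.6% if 40% is the null among evaluable subjects, and section 9.1 rules out no such reading. The synopsis can also be read as 39 dosed subjects in total, and then type I error is untouched and only power suffers.

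A reader might also take all six extra subjects to be dosed non-responders. Section 4.7.2 says 45 enrolled, not 45 dosed. Section 6.2 still requires eligibility to be met by Day 1, and the abstract and synopsis speak of evaluable eligible subjects. Some of the six may never take a dose. The 17.8% is therefore the result if all six are dosed failures, not a figure the protocol gives.

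Nor does the text show that every stop before cycle 6 is excluded. Section 8.3.1 needs one cycle and some re-evaluation, and the section 8.1 discontinuation visit may supply it. Section 9.3 also mentions a cycle 3 follow-up of these measures. What end-of-treatment assessments contain cannot be checked, because the body of Table 8-1 is not legible in the text available. The 30-day visit in section 6.4 lists no PRO, CBA or imaging. So later withdrawals drop out only if they are not re-evaluated.

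Finally, most of the protocol says 39 evaluable, and one sentence, stated twice, says otherwise. That makes the evaluable reading the likelier intention. It does not remove the contradiction, since that sentence claims to govern every analysis.

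**Conclusion.** The contradiction is real and bears on the trial's go/no-go decision. It must be resolved before the interim. The unequal handling of Cycle 1 toxicity or withdrawal and Cycle 1 progression is plain in section 8.3.1, and it can push the evaluable response rate upward.

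The size depends on assumptions the protocol does not settle. With corrected boundaries, the chance of a false positive runs from 4.6% (null defined among evaluable subjects) through 6.0% to 9.7% (one to three replaced dosed non-responders, 40% applying to all dosed) to 17.8% (six). Carrying a threshold of 21 over to 45 dosed gives 13.5%. With 39 dosed there is no inflation, only lost power. The printed boundaries are a distinct fault: correcting them would not settle the population, and settling the population would not correct them.

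**What to change.** State one primary efficacy set, in the same words, in sections 8.3.1, 9.1, 4.7.2 and 9.3 and in the synopsis: all subjects with at least one dose, counted in order of first dose and not replaced. This agrees with what 9.3 already says.

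- Count a dosed subject with no assessment usable for the cycle-6 endpoint as a non-responder, and say whether an end-of-treatment assessment made before cycle 6 is usable.
- Fix N and the boundary on that set: 7/16 then 21/39 (type I error 0.046, power 0.901), or 7/16 then 24/45 (0.039 and 0.91). Both powers are for a 65% rate among all dosed.
- Keep the 8.3.1 evaluable set as a supportive analysis.

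The change is to wording and boundaries only. The price is power: 65% must now hold among everyone dosed. If 13% are unassessed and 65% of the assessed respond, 56% of dosed subjects respond, and power is about 61% with 39 and 63% with 45. Going to 45 recovers little of that. If the sponsor expects such attrition, the alternative rate or the sample size should be set with it in mind. If the sponsor prefers the evaluable set as primary, the protocol should say that 40% and 65% refer to evaluable subjects, justify replacing early toxicity withdrawals, and amend the opening sentence of 9.3.
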